4.6 Questionnaires

Profile of Mood States (POMS) Questionnaire: The Profile of Mood States (POMS) is a widely used questionnaire for measuring distinct mood states. The POMS has 65 items, each with a 5-point adjective rating scale, which measures six identifiable moods or feelings: Tension-Anxiety (T), Depression-Dejection (D), Anger-Hostility (A), Vigor-Activity (V), Fatigue-Inertia (F) and Confusion-Bewilderment (C). Completion of the POMS takes 5-10 minutes.

DSM-5 Self-Rated Level 1 Cross-Cutting Symptom Measure: This questionnaire is delivered during the screening visit and assesses mental health domains that are important across psychiatric diagnoses. It consists of 23 questions that assess 13 psychiatric domains, including:

- Depression
- Anger
- Mania
- Anxiety
- Somatic symptoms
- Suicidal ideation
- Psychosis
- Sleep problems
- Memory
- Repetitive thoughts and behaviors
- Dissociation

- Personality functioning
- Substance use

Each item asks about how much (or how often) the individual has been bothered by the specific symptom during the past 2 weeks. Each item on the measure is rated on a 5-point scale. Cutoff scores, critical items, and follow-up measures are provided for each disorder. The questionnaire will be scored by a qualified member of the study team immediately after completion. If the subject scores above the cutoff for one or more disorders, these results will be discussed with a medically qualified team member, and a Clinical Center psychiatry consult will be obtained as appropriate.

Food Frequency Questionnaires (FFQ): Food Frequency Questionnaires (FFQ) are self-assessment questionnaires developed to identify foods and macronutrients that significantly contribute to energy intake [21]. Subjects will be given instructions to complete a form, which will be reviewed for completeness by clinic staff and any blank answers will be resolved. The FFQ contains questions on the frequency and portion size of consumption of certain food items over a defined period of time.

Three-Factor Eating Questionnaire: The three-factor eating questionnaire (TEFQ) is a self-assessment questionnaire developed to measure dietary restraint, disinhibition and hunger [22]. The questionnaire contains 36 items with a yes/no response, 14 items with a 1-4 response scale and 1 item with a 1-5 response scale.

MacArthur Socioeconomic Status (SES) Questionnaire: The MacArthur SES questionnaire is a widely used self-assessment questionnaire. It begins with subjective social status questions, followed by questions assessing educational attainment, occupational status, income and assets.

Owl and Lark Sleep Questionnaire: The Owl and Lark Sleep Questionnaire is a self-assessment questionnaire to determine morningness and eveningness in human circadian rhythms. The questionnaire contains 19 questions that require the subject to score based on wake and sleep habits.

Sleep Apnea Clinical Score (SACS): This questionnaire contains four items: measurement of neck circumference, history of hypertension, and two reported clinical symptoms (e.g. snoring, gasping during sleep). With these criteria, a sleep apnea clinical score (SACS) is generated, and a score greater than 15 indicates high risk for sleep apnea.

STOP-Bang Questionnaire: This questionnaire contains eight items, four of which are yes/no questions about snoring, tiredness, observed breathing during sleep, and blood pressure. The other four items are cut-off physical measurements and demographics (BMI, age, neck circumference, gender). Answering yes to three or more items indicates a high risk of OSA.

Hunger & Satiety Assessment: At several time points throughout the study, subjects will be asked to complete a survey to identify their perception of hunger (i.e., visual analog scale [VAS]) [22]. More specifically, the VAS survey will consist of four questions: 1) "How hungry do you feel right now?" 2) "How full do you feel right now?" 3) "How much do you want to eat right now?" and 4) "How much do you think you can eat right now?" Below each question on the

survey there is a horizontal 100mm line with qualifying statements such as “Not at all”/“The least I can possibly” and “Extremely”/“The most I can possibly”, anchoring the line on the extreme left and right side, respectively. In response to each question, subjects will be asked to draw a vertical mark on the horizontal line to represent the magnitude of their response to the question. A value for each response is quantified by measuring the distance of their mark (in mm) relative to the left end of the line. Therefore, the values (or "scores") for each question range from 0 to 100. On a few select days, data will be collected at least every 30 to 60 minutes over the next 2-3 hours after consuming each of their meals. It will take approximately 3 minutes for a participant to complete the assessment at a given time.

Sensory and palatability assessments: On several days throughout the study, subjects will be asked to complete a survey to assess the palatability and sensory properties (such as taste, texture, etc.) of the meals provided. Subjects will complete 100-point VAS line scale ratings of a series of measures, including meal liking and selected sensory properties. Survey items will be completed before eating, after the first bite, and after the participant has finished eating. Ratings include: how filling they expect a meal to be (expected fullness), how quickly or slowly they felt they ate the meal, and the extent to which they feel hungry, full and thirsty, their desire to eat and prospective consumption. The scale responses range from “Not at all” (0) to “Very” (100), except for prospective consumption, which is anchored by “Nothing at all” (0) and “The most I have ever eaten” (100). These ratings will be embedded amongst distracter “mood” ratings of alert, happy, and clear-headed. It will take approximately 3 minutes for a participant to complete the assessment at a given time.

4.7 Dual energy x-ray absorptiometry (DXA)

DXA scans will be performed at baseline followed by weekly scans using the General Electric Lunar iDXA (General Electric; Milwaukee, WI, USA) to determine body composition. Participants will change into a hospital gown, remove all metal-containing objects and lie on a table while the scanner, which emits low energy X-rays, passes along the body. The scan will take approximately 10 minutes. The radiation dose per scan is less than 1 mrem, and therefore the total of 5 scans planned per subject is below the guideline of 5000 mrem per year allowed for research subjects by the NIH Radiation Safety Committee. This is an FDA approved device that is being used as per approved labeling and parameters.

4.8 Physical activity monitoring

Physical activity will be quantified daily with an activity monitor using high sampling frequencies during all waking periods. Overall physical activity levels, daily changes, amount of time spent in sedentary, moderate, vigorous intensity categories and activity-associated energy expenditures will be extracted [23]. This device is an FDA cleared Class II medical device within the United States and is being used per approved labeling and parameters.

4.9 Oral glucose tolerance test

After an overnight fast, 75 grams of oral glucose will be administered. Blood samples will be obtained at 0, 10, 20, 30, 60, 90, 120, and 180 minutes to measure glucose and insulin concentrations. Blood samples for research will also be collected.

4.10 Continuous Glucose Monitoring (CGM)

Subjects will wear an FDA-approved CGM during their inpatient admission except during the MRS procedure. The device will be used to record glucose in real-time, approximately every 5 minutes. The system consists of a small sensor, transmitter, and hand-held receiver (about the size of a pager). The small sensor, with a small needle attached, will be inserted subcutaneously. The transmitter, which is attached to the sensor, will send the measured glucose to the receiver. The data stored in the receiver will be uploaded to a software for analysis. The sensor is changed at least once every two weeks. This is an FDA approved device that is being used as per approved labeling and parameters.

4.11 Sleep Monitor

The sleep scanner is a wearable tracking device intended for monitoring sleep patterns, which may affect metabolism. The sleep scanner collects data on respiratory effort, oxygen saturation, pulse, snoring, body position, and movement. This device consists of a sensor board, a respiratory belt (respiratory impedance plethysmography), and oximetry probe. Subjects will apply the respiratory belt around the diaphragm and oximetry probe clips to their finger. Subjects will be asked to apply the device at bedtime for several nights during the study period. The wearable tracking device is synced to a computer and data will be retrieved for analysis.

4.12 MRI/MRS

The subject will lie supine in the MR gantry and will be asked to hold their breath during scans. The duration will depend on their tolerance. The MR imaging test will be performed in collaboration with another NIH investigator, [name]. Subjects will undergo the MRI/MRS after signing a separate informed consent document specific to the imaging study, protocol 11-DK-168 ([name] study). This separate imaging study consent also involves CT scan. A CT scan of your heart may be performed to confirm findings from our MRI study. However, the CT scan portion is optional and refusal to undergo CT scan will in no way affect participation in the current study. MR spectroscopy will be performed primarily for assessment of hepatic fat content. Each MRI scan will last no more than 2 hours.

Gadolinium, a contrast agent sometimes administered to enhance visualization of the heart and blood vessels, will not be used during MR study scans. The MRI used in this study is FDA approved and it is being used as per approved labeling and parameters.

4.13 Saliva Collection

Variation in basic taste receptor genes (sweet, salty, sour, bitter, and umami) and nutrient sensing genes may contribute to differences in food preferences and dietary patterns. The taste receptor genes and their variants will be chosen accordingly for sweet and umami (T1R [taste receptor, type 1]), bitter (T2R [taste receptor, type 2]), and salty (ENaC [epithelial sodium channel][24]). The saliva sample will be collected using Orangene® (Genotek, Kanata, Canada) and used for the isolation of genomic DNA. Genomic DNA samples will be used as a template in TaqMan® assays (Applied Biosystems, Foster City, CA) in duplicates. Genotyping will be done by investigators blind to any subject information. Samples will be stored in a -80 °C freezer. For genotype quality assurance, the concentration of DNA in stored samples will be checked using a Nanodrop® Spectrophotometer ND100 prior to use. The observed genotypes will be checked for Hardy–Weinberg equilibrium. The exploratory analysis will investigate the relationship of taste and obesity-related genotype with dietary intake, and with sweet and salt preference and

thresholds. An analysis of variance will test whether taste detection thresholds or preference differ by genotype. Saliva collection takes approximately 2 minutes to complete. This procedure will be conducted at the beginning of the study period.

4.14 Psychophysical Taste Task: Sucrose and Salt Detection Thresholds

Sucrose and salt detection thresholds will be assessed using a two-alternative forced-choice staircase procedure was developed at the Monell Center for Adults [25-27]. The two-alternative forced choice is a psychophysical method developed to elicit responses about an individual's experience regarding a stimulus. It focuses on the evaluation of a single attribute (e.g., sweetness or saltiness), and the stimulus is adjusted based on the individual's responses [28, 29]. For this study, all testing will take place in a private, comfortable room. Subjects will be fasted for at least one hour before the task and acclimate to the testing room and to the researcher for approximately 15 minutes before testing. For the first trial and each subsequent trial, subjects will be presented with pairs of solutions in random order; within each pair, one solution will be distilled water, and the other will be the taste stimulus. Subjects will be instructed to taste the first solution presented within the pair, swish the solution in their mouth for 5 seconds, and expectorate. This will be repeated for the second solution within the pair. Between solutions, subjects will rinse their mouth with water; they will rinse once within a pair, and twice between successive pairs. After tasting both solutions within a pair, subjects will be asked to point to the solution that has a non-neutral taste. A tracking grid will be used to record subjects' responses [30-32]. This method eliminates the need for a verbal response and has been shown to be an effective method for assessing both taste and olfaction in children [30, 33]. The task takes approximately 30 minutes to complete. Participants will complete this task at the end of each test diet period.

4.15 Psychophysical Taste Task: Sucrose and Salt Preference

Sucrose and salt preference will be assessed using a two-series paired comparison-tracking method developed at the Monell Center for Adults [25-27]. Subjects will be presented with pairs of solutions differing in sucrose concentration (3, 6, 12, 24, and 36 g per 100 mL) and salt (0.92–6.14% wt/vol NaCl). They will be asked to taste the solutions without swallowing and point to which of the pair they liked better. Subsequently, each pair presented will be determined by the subject's preceding preference choice. The entire task is then repeated with the stimulus pairs presented in reverse order. After completion of the taste task, the geometric mean of the sucrose and salt concentrations chosen will be determined. This serves as an estimate of the participant's most preferred level of salt or sucrose [33, 34]. The task takes approximately 15 minutes to complete. Participants will complete this task at the end of each test diet period.

4.16 Above-threshold or Suprathreshold sensory function

Subjects will be trained on the use of the general labelled magnitude scale (gLMS) before we measure perceived intensities. Two trials consisting of 4 ascending concentrations of each stimulus (sucrose, NaCl) with the first "concentration" being water will be presented to the subjects. All four concentrations will be presented in random order without repeat. We will use 0.00, 0.09, 0.35, and 1.05 mol/l sucrose solutions and 0.00, 0.16, 0.38, and 1.05 mol/l salt solutions. Subjects will rate the perceived intensity of the stimulus using the gLMS scale and mean intensities of the two trials at each concentration for each stimulus to evaluate subjects' taste intensity perception.

The task takes approximately 10 minutes to complete. Participants will complete this task at the end of each test diet period.

4.17 Slips-of Action Paradigm

Goal-directed behaviors are guided by the assessment and valuation of possible outcomes. Thus, if the outcome of a certain behavior is devalued, the behavior is less likely to be performed. Habit responding occurs when an individual's actions are driven by external stimuli, which trigger and automatic behavioral response. This task assesses such learning in three stages: control discrimination training, congruent discrimination training, and an incongruent conflict task. In the initial stage if subjects respond correctly to the cue box instructions they will receive a reward. For the second stage, no feedback will be provided for correct or incorrect responses. This stage of the task should be controlled predominantly by a goal-directed system. The third stage features a conflict between the previously associated cues and outcomes. The total task time will be 27 minutes. Participants may complete this computer based task during the inpatient admission, depending on time.

4.18 Reward Prediction Error

A computerized probabilistic procedural learning task, the Probabilistic Selection Task, to assess participants ability to learn from both positive and negative outcomes. Dopamine plays a key role in reinforcement learning. Learning from positive outcomes is thought to be a result of phasic bursts firing of dopamine which stimulates the D1R direct ("Go") pathway and inhibits the D2R indirect pathway ("Stop"). The dip in dopaminergic firing experienced as a result of negative outcomes is thought to support learning to avoid the unrewarded choice. This task trains participants on reward contingencies and then tests their learning strategy to determine whether they are more adept at learning predominantly from positive feedback (suggestive of high phasic dopamine response) or from negative outcomes (suggestive of sufficient degree of dip in phasic and tonic dopamine response). Both phases of the task combined last approximately 25 minutes. Participants may complete this computer based task during the inpatient admission, depending on time.

5. Statistical Analysis

Day to day variability of *ad libitum* energy intake has a standard deviation of about 500-600 kcal/d [35-37]. Therefore, over a 14-day diet period each subject will have a mean energy intake with a standard error of about 130-160 kcal/d and the mean energy intake difference between the study diets will have a standard error of about 190-230 kcal/d. Using the conservative assumption that within-subject energy intake correlations are zero, the 20-subject study cohort will have an 80% power to detect a difference in mean *ad libitum* energy intake between the diets of about 125-150 kcal/d with a Type I error probability of 0.05.

Previous *ad libitum* diet studies comparing mean energy intake between 14 day periods consuming diets differing in macronutrient content have observed differences >250 kcal/d [12, 13] which is greater than the minimum detectable difference for a 10-subject cohort under the same assumptions as above. Therefore, the 20-subject cohort of our study is adequately powered to detect physiologically significant differences in *ad libitum* mean energy intake between the diets.

6. Safety Considerations

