Previous studies in similar numbers of subjects have shown changes in insulin sensitivity after 2-4 weeks of consuming diets that differ in advanced glycation end products that are produced through high heat cooking typical of industrially ultra-processed foods [14, 15]. One study suggested that consumption of meals composed of processed foods results in lower energy expenditure compared to consuming unprocessed foods [16]. Hepatic triglyceride content can also be altered with isocaloric diet changes in as little as 9 days [17]. Therefore, we will explore changes in glucose tolerance, various inflammatory markers, energy expenditure, and body composition metrics as follows:

2.2 Exploratory Aims:

1. To determine changes in oral glucose tolerance after 2 weeks of consuming an ultra-processed diet as compared to 2 weeks of consuming an unprocessed diet matched for presented calories, macronutrient composition, sugar, fiber, and sodium.
2. To determine differences in immune system function and inflammatory markers (c-reactive protein, E-selectin, soluble intercellular adhesion molecule-1, soluble vascular adhesion molecule-1, serum amyloid A, tumor necrosis factor- α , and interleukins 6 and 8) after 2 weeks of consuming an ultra-processed diet as compared to 2 weeks of consuming an unprocessed diet matched for presented calories, macronutrient composition, sugar, fiber, and sodium.
3. To determine changes in body weight and body composition after 2 weeks of consuming an unprocessed diet matched for presented calories, macronutrient composition, sugar, fiber, and sodium.
4. To determine changes in energy expenditure and substrate metabolism after 2 weeks of consuming an ultra-processed diet as compared to 2 weeks of consuming an unprocessed diet matched for presented calories, macronutrient composition, sugar, fiber, and sodium.
5. To determine changes in hepatic triglyceride content after 2 weeks of consuming an ultra-processed diet as compared to 2 weeks of consuming an unprocessed diet matched for presented calories, macronutrient composition, sugar, fiber, and sodium.

2.3 Second Cohort The first cohort of 20 subjects completed this study in late 2018 and the ultra-processed diet significantly increased energy intake by 508 kcal/d ($p=0.0001$) compared

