to the unprocessed diet – an effect that was not significantly related to sex or BMI. The increased energy intake was due to excess consumption of dietary carbohydrate and fat, but protein intake was stable between the diets.

The hypothesized mechanisms for the effect of the ultra-processed diet on energy intake include:

- i) The non-beverage energy density of the meals (calories per unit mass) was higher during the ultra-processed versus the unprocessed diet (1.96 kcal/g versus 1.06 kcal/g, respectfully). Therefore, more calories were consumed for a similar mass of food eaten;
- ii) The ultra-processed meals were consumed more rapidly which may have delayed satiety; and
- iii) The protein content of the ultra-processed diet was very slightly lower than the unprocessed diet (14% versus 15.6% of total calories, respectively) which may have led to increased overall energy intake to match absolute protein intake according to the protein leverage hypothesis.

We propose enrolling a second cohort of 20 subjects who will be exposed to a reformulated ultra-processed diet that more closely matches the unprocessed diet regarding non-beverage energy density and protein content. The ultra-processed diet will continue to be matched in terms of daily calories, macronutrient composition, sugar, fiber, and sodium. The ultra-processed diet will be modified to include foods that are typically eaten more slowly. If these factors were the main reasons that original ultra-processed diet led to the observed ~500 kcal/d increase in energy intake over the unprocessed diet, then the reformulated ultra-processed diet should lead to a smaller difference in energy intake between diets. Except for dietary formulation, the study design, procedures, and primary and exploratory aims, will be identical in the 2 cohorts. We will also compare the differences in ad libitum energy intake between ultra-processed and unprocessed diets between cohorts 1 and 2.

3. Study Design

This is a randomized order crossover study of healthy adult volunteers to determine differences in *ad libitum* energy intake when consuming an ultra-processed vs. unprocessed diet matched for presented calories, macronutrient composition, sugar, fiber, and sodium.

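### Section 5's detectable difference of 125-150 kcal/d counts only day-to-day noise, leaves out variation between subjects in diet response, and was not updated with cohort 1's SD for the second cohort of 20

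*Combined protocol and SAP*

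**What the plan says.** Section 5 (Statistical Analysis) starts from a day-to-day SD of energy intake of about 500-600 kcal/d and reasons that "over a 14-day diet period each subject will have a mean energy intake with a standard error of about 130-160 kcal/d". It then says that "the mean energy intake difference between the study diets will have a standard error of about 190-230 kcal/d". The power claim follows: "Using the conservative assumption that within-subject energy intake correlations are zero, the 20-subject study cohort will have an 80% power to detect a difference" of about 125-150 kcal/d at a type I error of 0.05.

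For reassurance, the section cites earlier diet studies with differences above 250 kcal/d, "which is greater than the minimum detectable difference for a 10-subject cohort under the same assumptions as above", and concludes that "the 20-subject cohort of our study is adequately powered to detect physiologically significant differences in" mean energy intake.

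Section 2.3 (Second Cohort) reports that the first 20 subjects have finished, with 508 kcal/d more eaten on the ultra-processed diet (p = 0.0001). It continues: "We propose enrolling a second cohort of 20 subjects who will be exposed to a reformulated ultra-processed diet". If the suspected mechanisms were the main cause, "then the reformulated ultra-processed diet should lead to a smaller difference in energy intake between diets". The diet effect is also to be compared between cohorts 1 and 2. Section 5 refers to one 20-subject cohort and does not mention cohort 1's results.

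**The concern.** The 190-230 kcal/d is the standard error with which one subject's own diet difference is measured. Section 5 uses it as the whole SD of that difference across subjects. This is correct only if every subject has the same true response. Any real variation in response adds to the SD and raises the detectable difference.

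Calling zero correlation conservative does not make up for this. For two diet means, zero correlation is cautious when it is applied to the full spread of subjects' mean intakes. Here it is applied to a standard error from which that spread has already been removed. If the phrase refers to correlation between days, the documents do not show which way the assumption errs.

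What is at stake is the reading of cohort 2. This is the only power statement in the document. A small or null cohort 2 result could be judged against 125-150 kcal/d and taken to mean that reformulation removed the effect, when the trial might not have been able to see a moderate one. The cohort comparison, which bears on the mechanism question, has no power or precision statement at all.

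**Working it through.** **Inputs.** From Section 5: daily SD 500-600 kcal/d, 14 days per diet, n = 20, 80% power, α = 0.05 (sidedness not stated; two-sided reproduces the plan). From Section 2.3: cohort 1 difference 508 kcal/d, p = 0.0001, n = 20; cohort 2 n = 20. No document gives a between-subject SD of the true diet response, so that is varied below as an assumption, *s*.

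**1. The plan's own figure.** 500/√14 = 133.6 and 600/√14 = 160.4. Multiplying by √2 gives 189.0 and 226.8. For a paired t-test (noncentral t, two-sided 0.05, 80% power) the detectable difference is 0.660 × SD at n = 20 and 0.996 × SD at n = 10.

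- n = 20: 124.8-149.8 kcal/d, matching the stated 125-150.
- n = 10: 188.2-225.9 kcal/d, below 250 as stated.

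Since the noise term alone gives the stated result, no other variance term is in it.

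**2. Adding variation in response.** SD = √(s² + 2 × daily SD²/14). This step does not use cohort 1's p-value.

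| Assumed s (kcal/d) | SD, daily SD 500 / 600 | Detectable, n = 20 |
|---|---|---|
| 0 | 189.0 / 226.8 | 125-150 |
| 100 | 213.8 / 247.8 | 141-164 |
| 200 | 275.2 / 302.4 | 182-200 |
| 300 | 354.6 / 376.1 | 234-248 |
| 400 | 442.4 / 459.8 | 292-304 |

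The 10-subject figure reaches 250 at SD 251.0, which is s = 108 (daily SD 600) to 165 (daily SD 500). The 20-subject figure reaches 250 at SD 378.5, which is s = 303 to 328.

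**3. Independence of days.** With an assumed first-order autocorrelation of -0.2 or +0.2 over 14 days, the variance of a period mean changes by a factor of 0.687 or 1.455. The 125-150 then becomes 103-124 or 151-181. The documents do not say which applies.

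**4. What cohort 1 implies, if its p-value came from a two-sided paired t-test (19 df).** t = 4.897, SE = 508/4.897 = 103.7, SD = 103.7 × √20 = 464 kcal/d (chi-square 95% interval 353-678). Rounding of p (0.00005 to 0.00015) moves the SD to 436-482. With an SD of 189-227, t would have been 10 to 12 and p about 5 × 10⁻⁹ to 3 × 10⁻¹⁰.

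| Quantity | At SD 464 | Over SD 353-678 |
|---|---|---|
| Detectable, n = 20 | 306 | 233-447 |
| Detectable, n = 10 | 462 | 351-675 |
| 95% CI half-width, n = 20 | 217 | 165-317 |
| Power at 150 | 28% | 44% to 16% |
| Power at 250 | 63% | 85% to 35% |
| Power at 508 | 99.6% | >99.9% to 89% |

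**5. Dependence on the test.** For a signed-rank test with normal approximation at n = 20, the largest possible z is 105/√717.5 = 3.92, so p cannot fall below 8.9 × 10⁻⁵. Under that test, p = 0.0001 is what an SD of 190-230 would produce and is no evidence against it. In simulation (normal differences, mean 508), p printed as 0.0001 in 99.9% of trials at SD 189 and 97.7% at SD 230. Under a t-test or an exact signed-rank test the share was at most 0.1% at those SDs.

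**6. Cohort 1 versus cohort 2** (two-sample t, 38 df, equal SDs assumed; detectable change 0.909 × SD). On the plan's SD this is 172-206 kcal/d. At SD 464 it is 422 kcal/d (321-616), with about 39% power if reformulation halves the effect to 254 kcal/d.

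**The case against.** The strongest reply is that Section 5 is not miscalculated and that its 20-subject conclusion passes its own benchmark unless cohort 1's p-value is brought in. The detectable difference stays below 250 kcal/d until the response SD exceeds 303-328, and at an assumed 200 the power at 250 is still 94-97%. The severe figures all need the p-value to come from a t-type test, and the document names none. This stands. It limits what can be said about size, but it does not supply the missing variance term.

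Two further points stand in part. The adjective 'conservative' qualifies one assumption, not the whole calculation, so naming the correlation meant would answer part of that complaint. Cohort 2's SD may also differ from cohort 1's; if reformulation shrinks the effect, variation in response may shrink too. That argues for showing a range, not for keeping an SD that assumes no variation.

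It is also true that no passage commits the sponsor to reading a null cohort 2 result against 125-150, that no 10-subject cohort is planned, and that cohort 1 had ample power for an effect as large as 508. The concern is therefore confined to smaller effects and to the cohort comparison.

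**Conclusion.** The concern holds. Section 5 uses measurement noise as the full SD of the paired differences, so 125-150 kcal/d is a best case with respect to variation in diet response. That conclusion needs no assumption about cohort 1. The 10-subject reassurance fails once the response SD exceeds 108-165 kcal/d; the 20-subject figure stays under 250 kcal/d up to 303-328.

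The size for cohort 2 is uncertain. If cohort 1's p-value is from a paired t-test and cohort 2 has the same SD, the detectable difference is about 306 kcal/d (233-447) and the detectable change between cohorts about 422 kcal/d (321-616). If it is from a normal-approximation signed-rank test, the published result does not contradict 190-230. Any excess variance need not all be varied response; period effects or correlation between days could contribute. In every case the plan does not use the SD that the sponsor now has, and 125-150 kcal/d is not a supported statement of power for cohort 2.

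**What to change.** Replace the planning SD in Section 5 with cohort 1's observed SD of the within-subject diet difference. It contains all sources of variance, so no component formula is needed. Suggested text:

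> In cohort 1 the SD of the within-subject diet difference in mean energy intake was [X] kcal/d (95% CI [..]; p-value from [test]). Assuming the same SD in cohort 2, 20 subjects give 80% power for a difference of [Y] kcal/d, [W]% power at 250 kcal/d, and an expected 95% CI half-width of [Z] kcal/d. The cohort 1 versus cohort 2 comparison has 80% power for a change of [V] kcal/d.

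If X were 464, then Y = 306, W = 63, Z = 217 and V = 422; these are placeholders until the actual SD is inserted. Giving Y, Z and V at the limits of the SD's confidence interval as well would allow for cohort 2's SD being different. Remove 'conservative', and delete or recompute the 10-subject and adequacy sentences.

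The cost is a wording change from data already held. It adds no subjects and leaves design, endpoint and analysis as they are. The only downside is a less favourable stated figure if the actual SD exceeds 190-230 kcal/d.
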